### **Causality**

**Not related or improbable:** a clinical event including laboratory test abnormality with temporal relationship to trial treatment administration which makes a causal relationship incompatible or for which other drugs, chemicals or disease provide a plausible explanation. This will be counted as “unrelated” for notification purposes.

**Possible:** a clinical event, including laboratory test abnormality, with temporal relationship to trial treatment administration which makes a causal relationship a reasonable possibility, but which could also be explained by other drugs, chemicals, or concurrent disease. This will be counted as “related” for notification purposes.

**Probable:** a clinical event, including laboratory test abnormality, with temporal relationship to trial treatment administration which makes a causal relationship a reasonable possibility, and is unlikely to be due to other drugs, chemicals, or concurrent disease. This will be counted as “related” for notification purposes.

**Definite:** a clinical event, including laboratory test abnormality, with temporal relationship to trial treatment administration which makes a causal relationship a reasonable possibility, and which can definitely not be attributed to other causes. This will be counted as “related” for notification purposes.

An AE whose causal relationship to the study IMP is assessed by the Chief Investigator as “possible”, “probable”, or “definite” is an Adverse Drug Reaction.

With regard to the criteria above, medical and scientific judgment shall be used in deciding whether prompt reporting is appropriate in that situation.

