## **SUSARs**

**A serious adverse event that is either sudden in its onset (anaphylaxis), unexpected in its severity and seriousness or not a known side effect of the IMP *and* related or suspected to be related to the IMP is classed as Suspected Unexpected Serious Adverse Reaction and requires expedited reporting as per the clinical trials regulations.**

**All serious adverse events that fall or are suspected to fall within these criteria shall be treated as a SUSAR until deemed otherwise.**

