**Table 8. Serious adverse events for GTN in relationship to the study.**

Data are number (%).

SAEs up to day 90					Fatal SAEs up to day 90				
	All	GTN	Sham	Difference (p)		All	GTN	Sham	Difference (p)
Number SAEs	xxx	xxx	xxx		Number SAEs	xxx	xxx	xxx	
Treatment time									
...Before		xxx	xxx (xxx)	BLR	Before		xxx	xxx (xxx)	BLR
...During	xxx	xxx (xxx)	xxx (xxx)	BLR	During	xxx	xxx (xxx)	xxx (xxx)	BLR
...After	xxx	xxx (xxx)	xxx (xxx)	BLR	After	xxx	xxx (xxx)	xxx (xxx)	BLR
Relationship to treatment									
...Not related	xxx	xxx (xxx)	xxx (xxx)	Chi-sq/FET	Not related	xxx	xxx (xxx)	xxx (xxx)	Chi-sq/FET
...Improbable	xxx	xxx (xxx)	xxx (xxx)	-	Improbable	xxx	xxx (xxx)	xxx (xxx)	-
...Possible	xxx	xxx (xxx)	xxx (xxx)	-	Possible	xxx	xxx (xxx)	xxx (xxx)	-
...Probable	xxx	xxx (xxx)	xxx (xxx)	-	Probable	xxx	xxx (xxx)	xxx (xxx)	-
...Definite	xxx	xxx (xxx)	xxx (xxx)	-	Definite	xxx	xxx (xxx)	xxx (xxx)	-

[figure not shown]

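### An SAE with compatible timing and a plausible alternative explanation meets both the 'Not related or improbable' and the 'Possible' definition, with no tie-break, so its relatedness is undetermined

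*Protocol*

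**What the plan says.** The protocol (Adverse Events, Causality) gives four classes.

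- *Not related or improbable*: an event whose temporal relationship to treatment is one "which makes a causal relationship incompatible or for which other drugs, chemicals or disease provide a plausible explanation". The consequence follows: "This will be counted as “unrelated” for notification purposes".
- *Possible*: an event with timing "which makes a causal relationship a reasonable possibility, but which could also be explained by other drugs, chemicals, or concurrent disease". It is counted as related.
- *Probable*: causation is a reasonable possibility and the event "is unlikely to be due to other drugs, chemicals, or concurrent disease". It is counted as related.
- *Definite*: causation is a reasonable possibility, for an event "which can definitely not be attributed to other causes". It is counted as related.

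The same section makes an event an adverse drug reaction if the Chief Investigator grades it possible, probable or definite. The SUSARs section requires, besides unexpectedness, that the event be "related or suspected to be related to the IMP is classed as Suspected Unexpected Serious Adverse Reaction". SAP Table 8 tabulates SAEs and fatal SAEs by arm under "Relationship to treatment", with separate rows for *Not related* and *Improbable*, although the protocol gives those two one joint definition.

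**The concern.** A causality scale should give each event one class. Here the lowest class can be entered by either of two routes, and the second route (another plausible explanation) does not require that GTN be an unlikely cause. *Possible* is built on the same feature: GTN could have caused the event, and so could something else. Two neighbouring classes therefore claim the same event, and they fall on opposite sides of the line between unrelated and related.

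Safety is a stated aim of this trial. For events in the overlap, the adverse drug reaction count, the relatedness part of a SUSAR decision and the relationship rows of SAP Table 8 would depend on which definition the assessor applied, because the text supports both.

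**Working it through.** The plan gives no figure to reproduce, and no rate or sample size is involved. The check is a logic table, followed by a cross-match of two lists in the protocol.

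**Step 1: apply the four definitions to every combination.** Timing has two states (incompatible with causation; causation a reasonable possibility). The alternative explanation has three (plausible; unlikely; ruled out). This gives 2 × 3 = 6 combinations.

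| Timing | Alternative explanation | Classes met as written |
|---|---|---|
| Incompatible | Plausible | Not related or improbable |
| Incompatible | Unlikely | Not related or improbable |
| Incompatible | Ruled out | Not related or improbable |
| Reasonable possibility | Plausible | **Not related or improbable, and Possible** |
| Reasonable possibility | Unlikely | Probable |
| Reasonable possibility | Ruled out | Definite |

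One combination of six receives two classes. *Probable* and *Definite* do not overlap with the lowest class, because each excludes a plausible alternative. An event with incompatible timing is unambiguous whatever else might explain it.

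**Step 2: look for a tie-break.** The Causality section closes with an appeal to medical and scientific judgement, but about whether prompt reporting is appropriate. It does not say which class prevails when two apply.

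**Step 3: ask whether the overlap combination is likely to arise.** Protocol Table 3 lists 13 known side effects of the GTN patch.

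- Systemic, 8 terms: headache, dizziness, tachycardia, orthostatic hypotension, flushing, nausea, vomiting, heart rate increase. All 8 have a counterpart in Appendix K's list of events expected after stroke, reading orthostatic hypotension as hypotension and heart rate increase as tachycardia.
- Skin and application site, 5 terms: contact dermatitis, erythema, pruritus, burning, irritation. None is in the after-stroke list by name.

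8 + 5 = 13. For the systemic reactions the protocol itself supplies the competing explanation. The *other drugs* route works the same way. The Known Side Effects section says antihypertensives may potentiate the blood pressure effect of GTN, and the section on concomitant treatments prohibits none. The background section puts the fall in systolic pressure at 15, 60 and 120 minutes and peak concentrations at 1–2 hours, so compatible timing is also to be expected.

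**Step 4: trace what depends on the class.**

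| Item | Depends on the causality class? |
|---|---|
| Adverse drug reaction status (Causality) | Yes |
| Relatedness part of SUSAR classification | Yes |
| SAP Table 8, relationship rows | Yes |
| SAE report to the Chief Investigator within 24 hours | No, all SAEs |
| Annual report to the MHRA and REC | No, all SAEs |
| Endpoint of any SAE by day 2; SAP Table 9 | No, all SAEs |

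**Step 5: test candidate repairs on the same table.**

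- Replacing *or* with *and* in the lowest class removes the overlap, but leaves incompatible timing with an unlikely or excluded alternative (2 of 6) in no class.
- Reserving the lowest class for incompatible timing or no reasonable possibility of causation, with *Possible* as the minimum otherwise, gives 0 of 6 double-classified and 0 of 6 unclassified.

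**The case against.** The strongest case on the other side is that this is a wording ambiguity with limited consequences. Several of its points stand.

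- A reader might infer that events filed as unrelated go unnotified. The documents do not support this. Under Reporting of adverse events, every SAE reaches the Chief Investigator within 24 hours and enters the annual report. The SUSARs section treats suspected cases as SUSARs until deemed otherwise.
- A reader might infer that an event called unrelated is never assessed for expectedness. The protocol lists seriousness, expectedness and causality together, both in the Definitions and in the Chief Investigator's SUSAR duties, and states no sequence.
- For events listed in Appendix K, such as hypotension or neurological deterioration, expedited reporting is already switched off. Relatedness changes it only when severity or seriousness is unexpected.
- The Chief Investigator determines causality with the treating practitioners. This central role should make grading more uniform than separate decisions by sites.
- The adverse event definition leaves out manifestations of the stroke itself unless they are worse than expected, which removes some stroke-explained events.
- A reader might infer that the related-SAE count is biased low, or could range from near zero to most SAEs. The documents give no figure from which either could be computed. Nor do they say that the DMC relies on a related-SAE count; it reviews unblinded safety data, including SAEs and neurological deterioration.

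It can also be argued that supplying a plausible explanation is a stronger condition than merely being able to explain an event, so that the classes are graded. But anything that plausibly explains an event can also explain it, and the text sets no threshold between the two.

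These points limit the reach. The safeguards secure that SAEs are captured and reported; they do not give an overlapping event one class. A single adjudicator still has two applicable definitions with opposite consequences.

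**Conclusion.** The Causality section contradicts itself for one type of event: an SAE for which timing makes causation a reasonable possibility and another explanation is plausible. It is both unrelated and related as the definitions stand. The overlap is one of six combinations, but probably a frequent one in acute stroke, since 8 of the 13 side-effect terms in protocol Table 3, and all the systemic ones, have after-stroke counterparts in Appendix K. It would be too much to say that almost any GTN reaction is affected: the 5 skin and application-site terms have no such counterpart by name.

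What is left undetermined is adverse drug reaction status, the relatedness part of the SUSAR decision (mainly for events outside Appendix K or of unexpected severity) and the relationship rows of SAP Table 8. The comparison of all SAEs between arms is intact.

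The conclusion rests on a literal reading of the definitions and on taking Appendix K as the protocol's own view of what stroke can explain. The number of SAEs affected cannot be estimated from the documents.

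**What to change.** In the protocol's Causality section and the SAE form guidance:

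1. Reserve *Not related or improbable* for events with incompatible timing or with no reasonable possibility of a causal relationship to trial treatment.
2. State that an event with a reasonable possibility of a causal relationship is classed at least *Possible*, even when another explanation exists.

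The rule should rest on reasonable possibility, not on timing alone. Non-fatal SAEs are collected only to 48 hours after the first patch, so a timing-only rule would move most of them into *Possible* and make the related count uninformative in the other direction.

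In SAP Table 8, merge the *Not related* and *Improbable* rows, or define each separately in the protocol. This does not change the related count, since both count as unrelated; it gives every row a definition.

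The cost is a short edit to the protocol, the form guidance and one SAP table. Somewhat more SAEs will be counted as possibly related.

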### **Reporting of adverse events**

Participants will be asked to contact the study site immediately in the event of any serious adverse event. All adverse events will be recorded and closely monitored until resolution, stabilisation, or until it has been shown that the study medication or treatment is not the cause. The Chief Investigator (delegated responsibility by the Sponsor) shall be informed immediately (within 24 hours) of any serious adverse events and shall determine seriousness and causality in conjunction with any treating medical practitioners.

Where it is the partner of trial participant, consent will be obtained for this observation from both the partner and the medical practitioner.

All serious adverse events will be recorded and reported to the MHRA and REC as part of the annual Development Safety Update Reports. SUSARs will be reported within the statutory timeframes to the MHRA, and REC as stated below. The Sponsor shall ultimately be responsible for adverse event reporting.

### **Urgent Safety Measures**

An Urgent Safety Measure is a procedure taken to protect a research participant when that participant is identified as being at risk of harm in relation to their involvement in a research

project and urgent action, which deviates from the approved protocol, is required to manage the event, and protect the participant.

Any urgent safety measure relating to a Clinical Trial of an Investigational Medicinal Product (CTIMP) should be communicated to the MHRA immediately. They advise that sponsors phone the MHRA Clinical Trial Unit and discuss the event with a safety scientist. The sponsor must then follow-up with notification in writing within three days of the action being taken. The notification should be in the form of a substantial amendment and should describe the event, the measures taken and justification for the measures taken.

## **SUSARs**

**A serious adverse event that is either sudden in its onset (anaphylaxis), unexpected in its severity and seriousness or not a known side effect of the IMP *and* related or suspected to be related to the IMP is classed as Suspected Unexpected Serious Adverse Reaction and requires expedited reporting as per the clinical trials regulations.**

**All serious adverse events that fall or are suspected to fall within these criteria shall be treated as a SUSAR until deemed otherwise.**

**The event shall be reported immediately (within 24 hours) of knowledge of its occurrence to the Chief Investigator.**

**The Chief Investigator will:**

- Assess the event for seriousness, expectedness, and relatedness to the study IMP.
- Take appropriate medical action, which may include halting the trial and inform the Sponsor of such action.
- If the event is deemed a SUSAR, shall, within seven days, enter the required data on the MHRA's eSUSAR web site.
- Shall inform the REC using the reporting form found on the HRA web page within 7 days of knowledge of the event.
- Shall, within a further eight days send any follow-up information and reports to the MHRA and REC.
- Make any amendments as required to the study protocol and inform the ethics and regulatory authorities as required.

## **Trial Treatment Related SAEs**

**A serious adverse event that is unexpected in its severity and seriousness *and* deemed directly related to or suspected to be related to the trial treatment but not the IMP shall be reported to the ethics committee that gave a favourable opinion as stated below.**

**The event shall be reported immediately of knowledge of its occurrence to the Chief Investigator.**

**The Chief Investigator will:**

- Assess the event for seriousness, expectedness, and relatedness to the trial treatment.

- Take appropriate medical action, which may include halting the trial and inform the Sponsor of such action.
- If the event is deemed related to the trial treatment shall inform the REC using the reporting form found on the HRA web page within 7 days of knowledge of the event.
- Shall, within a further eight days send any follow-up information and reports to the REC.
- Make any amendments as required to the study protocol and inform the REC as required.

### **Participant removal from the study due to adverse events**

Any participant who experiences an adverse event may be withdrawn from the study at the discretion of the Investigator. Should the participant not receive the complete intervention due to, for example, an (serious) adverse drug reaction, they will remain in the study until the end of the trial at day 90 ( $\pm 30$ ), as completeness of follow-up is essential. However, should they wish to do so, any participant is free to withdraw from the trial at any time and without giving a reason.

## **ETHICAL AND REGULATORY ASPECTS**

### **ETHICS COMMITTEE AND REGULATORY APPROVALS**

The trial will not be initiated before the protocol, informed consent forms and participant and GP information sheets have received approval / favourable opinion from the Medicines and Healthcare products Regulatory Agency (MHRA), Research Ethics Committee (REC), the respective National Health Service (NHS) or other healthcare provider's Research & Development (R&D) department, and the Health Research Authority (HRA) if required. Should a protocol amendment be made that requires REC approval, the changes in the protocol will not be instituted until the amendment and revised informed consent forms and participant and GP information sheets (if appropriate) have been reviewed and received approval / favourable opinion from the REC and R&D departments. A protocol amendment intended to eliminate an apparent immediate hazard to participants may be implemented immediately providing that the MHRA, R&D and REC are notified as soon as possible, and an approval is requested. Minor protocol amendments only for logistical or administrative changes may be implemented immediately; and the REC will be informed.

The trial will be conducted in accordance with the ethical principles that have their origin in the Declaration of Helsinki, 1996; the principles of Good Clinical Practice, in accordance with the Medicines for Human Use Regulations, Statutory Instrument 2004, 1031 and its subsequent amendments and the UK Department of Health Policy Framework for Health and Social Care, 2017.

### **INFORMED CONSENT AND PARTICIPANT INFORMATION**

The process for obtaining participant informed consent will be in accordance with the REC guidance, and Good Clinical Practice (GCP) and any other regulatory requirements that might be introduced. The investigator or their nominee and the participant or other legally authorised representative (personal or professional) shall both sign and date the Consent Form before the person can commence follow-up on day 2.

The participant will receive a copy of the signed and dated forms and the original will be retained in the Trial Master File. A second copy will be filed in the participant's medical notes and a signed and dated note made in the notes that informed consent was obtained for the trial.

The decision regarding participation in the study is entirely voluntary. The investigator or their nominee shall emphasize to them that consent regarding study participation may be withdrawn at any time without penalty or affecting the quality or quantity of their future medical care, or loss of benefits to which the participant is otherwise entitled. No trial-specific follow-ups will be done before informed consent has been obtained.

The investigator will inform the participant of any relevant information that becomes available during the course of the study, and will discuss with them, whether they wish to continue with the study. If applicable they will be asked to sign revised consent forms.

If the Informed Consent Form is amended during the study, the investigator shall follow all applicable regulatory requirements pertaining to approval of the amended Informed Consent Form by the REC and use of the amended form (including for ongoing participants).

## **RECORDS**

### **Drug accountability**

Drug supplies will be kept in a secure, limited access storage area under the storage conditions specified by Pharmacy.

The investigator and the local site pharmacist shall maintain records of the study drug's delivery to the pharmacy, an inventory at the site, the distribution to each participant, and the return to the pharmacy or alternative disposition of unused study drugs. These records will include dates, quantities received, batch / serial numbers, expiration dates, and the unique code numbers (patient trial number) assigned to the trial participant. Investigators and /or the local site pharmacists will maintain records that document adequately that the participants were provided with the correct study medication. These records will be part of each patient's Case Report Form (CRF). All study medication packs and bottles received by the pharmacy shall be accounted for.

### **Case Report Forms**

Each participant will be assigned a trial identity code number, (centre number, participant number and initials) allocated at randomisation, for use on CRFs other trial documents and the electronic database. The documents and database will also use their initials (of first and last names separated by a hyphen or a middle name initial when available) and date of birth (dd/mm/yy) is entered into the database once for the use of data verification and is not visible when entering trial data.

CRFs will be treated as confidential documents and held securely in accordance with regulations. The investigator will make a separate confidential record of the participant's name, date of birth, local hospital number or NHS number, and Participant Trial Number (the Trial Recruitment Log), to permit identification of all participants enrolled in the trial in accordance with regulatory requirements and for follow-up as required.

CRFs shall be restricted to those personnel approved by the Chief or local Principal Investigator and recorded on the 'Trial Delegation Log.'

All paper forms shall be filled in using black ballpoint pen. Errors shall be lined out but not obliterated by using correction fluid and the correction inserted, initialled, and dated. The Chief or local Principal Investigator shall sign a declaration ensuring accuracy of data recorded in the CRF.

### **Source documents**

Source documents shall be filed at the investigator's site and may include but are not limited to, consent forms, current medical records, laboratory results and pharmacy records. A CRF may also completely serve as its own source data. Only trial staff as listed on the Delegation Log shall have access to trial documentation other than the regulatory requirements listed below.

### **Direct access to source data / documents**

The CRF and all source documents, including progress notes and copies of laboratory and medical test results shall be made available at all times for review by the Chief Investigator, Sponsor's designee and inspection by relevant regulatory authorities (MHRA).

